## 4.12 Interpretation rules

The outcomes of benefit (disease activity and damage progression) and harm (number of patients with at least one SAE or other AESI) will be interpreted simultaneously.

The outcomes of benefit will be interpreted as follows (prednisolone group compared to placebo; reference to the specific rejected null hypotheses in parentheses):

1. success:
  - a. lower disease activity ( $H_{0,1a}$ )  
AND lower damage score ( $H_{0,2a}$ )
  - b. lower disease activity OR lower damage score; AND confounding ( $H_{0,4a}$  or  $H_{0,4b}$ )
2. partial success/tradeoff:
  - a. lower disease activity OR lower damage score AND NO confounding
  - b. NO lower disease AND NO lower damage progression AND confounding
3. failure: NO lower disease activity AND NO lower damage score AND NO confounding.

The outcomes of harm will be interpreted as follows:

1. success: NO significant increase in AEs
2. failure: significant increase in AEs ( $H_{0,3a}$ )

Combined assessment of benefit and harm

- a. Success: success in benefit and harm
- b. Failure: failure in benefit and harm
- c. Partial success/tradeoff: all other scenarios

For further interpretation of increases in the occurrence of SAE or other AESI in the active treatment group that did not reach significance, we will use the suggestions of the GRADE (Grades of Recommendations, Assessment, Development, and Evaluation) Working Group (Guyatt 2012), upper limit of one-sided 95% confidence interval (CI):

1.  $> 1.3$ : GC associated with a trend towards greater occurrence;
2.  $\leq 1.2$ : GC appears to have little effect on the occurrence;
3.  $> 1.2$  and  $\leq 1.3$ : results failed to demonstrate or exclude a greater occurrence.

In the case of a numerical DECREASE in the occurrence of SAE or other AESI in the active treatment group, a more stringent test for significance will be performed ( $p < 0.025$ ).

For the interpretation of decreases that did not reach significance:

lower limit of one-sided 95% CI:

1.  $< 0.7$ : GC associated with a trend towards reduced occurrence;
2.  $\geq 0.8$ : appears to have little effect on the occurrence;
3.  $< 0.8$  and  $\geq 0.7$ : results failed to demonstrate or exclude a reduced occurrence.

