## 4.10 Modeling and estimating

The testing of the hypothesis sets requires estimating the average effect of treatment on benefit (operationalized as DAS28 and progression of joint damage) and harm (operationalized as encountering at least one SAE or other AESI). An observed effect with a probability of occurrence under the (one-sided) null hypothesis (p-value) of 5% or less will be considered significant causing us to reject the null and to accept the alternative hypothesis. The hypotheses and their tests are one-sided in view of pre-existing knowledge for benefit and the likelihood that true benefit will be underestimated in the context of the pragmatic design and potential differential co-intervention (see section 4.11); and for harm because of limited power. This results in a higher chance of declaring benefit, but also a higher chance of declaring harm.

The average effect of treatment on DAS28 (hypotheses 1) and damage progression (hypothesis 2) will be estimated in a mixed effects regression model. The exact form and empirical fit of the model are important determinants of the power of the statistical test of the treatment effect parameter, as described below. Hypotheses 3 require estimation of the difference in probability to encounter a SAE or other AESI between treatment and placebo over 24 months, which will be implemented by estimating the odds ratio of a SAE or other AESI in treatment versus placebo. All analyses will also take into account that the GLORIA study uses a stratified sampling design, where within each of 28 participating centers randomization is executed stratified by earlier exposure to glucocorticoids (yes/no) and start or switch of other anti-rheumatic drugs at the beginning of the trial.

We first describe how hypothesis testing for the GLORIA study will be executed. In this exposition, we assume that the observed data matrix is complete and that the estimated effects are not confounded with treatment changes. We describe methods to address incomplete data (section 4.2) and to assess confounding with treatment changes (section 4.11).

Our general analysis strategy can be summarized as follows:

1. Test hypotheses 1 to 3 with models described in this section and missing-at-random data correction (section 4.2).
2. Execute robustness checks for monotonous not-missing-at-random data pattern with non-responder imputation (NRI; section 4.2).
3. Assess confounding with treatment changes (section 4.11)

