## 6 Sample size and power calculations

In the main GLORIA trial, 225 patients per treatment group will be entered (total 450 patients).

In the chosen analysis strategy (see section 4), to detect differences in benefit (disease activity, radiographs) extensive RA trial experience (both for GC and other agents) has shown a sample size of 200 patients per group is amply sufficient. For example, in the CAPRA-2 study that compared modified release prednisone 5mg/d against placebo, the prednisone group had 231 patients, the placebo group 119 patients. The change in DAS28 after 3 months of treatment was  $-1.15$  in the prednisone group,  $-0.63$  in the placebo group; difference  $-0.52$  (SE 0.13,  $p<0.001$ ) (Buttgereit, 2013). However, the true incidence of adverse events (AEs) for GCs is currently unknown. Most relevant data to assess sample size adequacy for this study come from the reported CAMERA-2 trial (Bakker, 2012). This trial randomized 236 early RA patients to tight-control high-dose methotrexate plus 10 mg prednisolone or placebo for two years. Interestingly, 22% of placebo patients compared to only 14% of prednisolone patients reported at least one serious AE or clinical event as defined in our protocol.

The original protocol used a base case expectation for a total of 20% of patients experiencing at least one event over two years in the placebo group and calculated a need for 400 patients in each treatment group, to have about 80% power to detect an increase of 7% (from 20% to 27% events; 90% power for an increase of 9%). However, based on our current experience the sample can be decreased to about 450 instead of 800.

Elaboration:

In December 2018 we had >400 patients in the trial with a mean follow up of 9 months, and we had 84 cases with at least one serious adverse event or an event of special interest (the primary harm outcome). A simple extrapolation leads to an estimated rate of about 49% over 2 years (pooled over the whole blinded trial population, i.e. both treatment groups taken together). We have also performed life table analysis, which accounts for patients stopping prematurely; this analysis leads to an estimated rate of 40% (95% confidence interval: 30%-50%).

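### The prespecified 'trend' wording for non-significant harm results rests on the confidence limit farther from 1, which shows what is not excluded and is not evidence of an effect

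*SAP*

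**What the plan says.** SAP 4.10 tests harm one-sided at 5%: "An observed effect with a probability of occurrence under the (one-sided) null hypothesis (p-value) of 5% or less will be considered significant". SAP 4.12 then adds a further reading for results that miss significance, and Protocol 11.1 (prespecified interpretation rules) has the same bands.

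**Non-significant increases**, by the upper limit of the one-sided 95% interval:
- above 1.3: "GC associated with a trend towards greater occurrence"
- above 1.2 and up to 1.3: "results failed to demonstrate or exclude a greater occurrence"
- 1.2 or below: "GC appears to have little effect on the occurrence"

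**Numerical decreases**: "a more stringent test for significance will be performed", at p < 0.025. If that test fails, the lower limit of the one-sided 95% interval decides. Below 0.7 the label is "GC associated with a trend towards reduced occurrence", from 0.7 to below 0.8 the result is inconclusive, and at 0.8 or above it is little effect.

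No band uses the point estimate or the limit nearer to 1. The bands are attributed to the GRADE Working Group. Neither document reports how often each label would arise when there is no effect. SAP 4.12 does not state the scale of the limits: SAP 4.10 speaks of an odds ratio, while SAP 4.10.3 uses a log link to estimate relative risk.

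**The concern.** An upper limit above 1.3 beside a non-significant test means that a 30% increase has not been ruled out. It does not show that an increase is present. Yet this band carries the affirmative wording, while the band with the lower limit, where more has been excluded, is called inconclusive. For a fixed estimate, a wider interval therefore earns the stronger claim.

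What is at stake is how a co-primary outcome is described. A result that the same section counts as success on harm could also have to be reported as associated with a trend towards harm, on data that fit well with no effect. On the other side, a non-significant decrease could be described as a trend towards fewer events.

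**Working it through.** **Inputs.** 225 per arm (SAP 6), 1:1 allocation (Protocol 9.2), expected pooled event rate 40% with interval 30% to 50% (SAP 6), planned placebo rate 34% (SAP Table 1), one-sided 5% test (SAP 4.10), relative-risk scale (SAP 4.10.3), harm data assumed complete (SAP 4.2).

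**The plan's own figure.** SAP 6 gives 80% power for 34% against 46% with 400 patients. One-sided, without continuity correction: z = [0.12 − 1.645·√(2·0.40·0.60/200)] / √[(0.34·0.66 + 0.46·0.54)/200] = (0.12 − 0.0806)/0.0486 = 0.81, so power is 79.1%. This agrees with the plan to within rounding.

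**Where the label starts at 40%.** SE(log RR) = √[2(1−p)/(np)] = √[2·0.6/(225·0.4)] = 0.1155. The upper limit is the estimate times exp(1.645·0.1155) = 1.21. It passes 1.3 once the observed RR exceeds 1.3/1.21 ≈ 1.075. There z = ln(1.075)/0.1155 = 0.63 and one-sided p is about 0.27. Significance is reached at an RR of about 1.21, so every estimate between about 1.075 and 1.21 is called a trend.

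A concrete case: 94/225 against 87/225 gives RR 1.08, two-sided 90% CI 0.89 to 1.31, one-sided p 0.25. The rule calls this a trend towards greater occurrence.

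**How often, with no true effect.** By normal approximation at 40%: P(0.63 < Z < 1.645)/P(0 < Z < 1.645) = 0.215/0.45 = 48%. Exact enumeration of two independent binomials, with Wald limits on log RR, gives:

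| True rate, both arms | Increases labelled trend: share of non-significant increases (of all trials) | Decreases labelled trend: share of non-significant decreases (of all trials) |
|---|---|---|
| 30% | 88% (38%) | 40% (18%) |
| 34% | 73% (31%) | 27% (12%) |
| 40% | 50% (22%) | 12% (5%) |
| 50% | 19% (8%) | 0.2% (0.1%) |

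**When imprecision alone is enough.** Every non-significant increase is labelled a trend if 1.645·SE exceeds ln 1.3 = 0.262, that is SE > 0.1595. At 225 per arm this needs (1−p)/p > 0.1595²·225/2 = 2.86, so p below about 26%.

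**Dependence on precision with the estimate held fixed.** Observed RR 1.08 (41.6% against 38.5%):

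| Per arm | Upper limit | One-sided p | Label |
|---|---|---|---|
| 100 | 1.44 | 0.33 | trend |
| 225 | 1.31 | 0.25 | trend |
| 400 | 1.25 | 0.19 | inconclusive |
| 800 | 1.19 | 0.10 | little effect |

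The evidence for an increase strengthens down the table while the label weakens. The sample sizes other than 225 only illustrate how the rule behaves.

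**The case against.** - **Reading the upper limit is a deliberate caution about harm.** SAP 4.10 explains the lean towards declaring harm by limited power. Under the design alternative (34% against 46%, 225 per arm), exact enumeration puts 89% of non-significant increases in the trend band, so the label flags most missed harms. This supports keeping the limit and the thresholds. It does not make the wording true, and saying that an increase above 30% is not excluded gives the same warning.
- **The labels follow a cited source.** A reader might infer that the plan misapplies GRADE. The source is not in the documents, so this cannot be judged. Attribution does not change how often the labels arise under no effect.
- **The label is not triggered by imprecision alone.** This stands for the expected rate. Recruitment closed at 452, so precision is nearly fixed for a given event rate, and at 40% the observed RR must also exceed about 1.075.
- **Half is a conditional share.** This stands. A reader might infer that an inert drug gets the harm label in half of all trials; at 40% the figure is 22%.
- **Both directions are not equally affected.** This stands. ln 0.7 lies farther from zero than ln 1.3, and decreases are tested at 0.025. At 40%, about 43% of the decrease labels have z between −1.645 and −1.96, where a two-sided 90% interval already excludes 1.
- **No verdict depends on the bands.** This stands. Success or failure on harm, and the combined assessment, rest on significance only. A reader might infer that the trial's conclusion is at risk, but SAP 4.12 does not support that.

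**Conclusion.** The point holds for the wording. In both directions the rule that triggers the trend labels cannot support an affirmative claim of association. With no true effect and 225 per arm, the label attaches to 50% of non-significant increases at the expected 40% rate. Over the plan's own 30% to 50% interval for that rate, the share runs from 88% to 19%. For decreases the problem is real but smaller.

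The defect is confined to the prespecified further interpretation of the co-primary harm outcome; the tests and verdicts stand. It is worth correcting because the misdescription is foreseeable and the correction is cheap.

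The figures assume the relative-risk scale, equal arms, complete harm data and independent patients. The centre random effect and strata of SAP 4.10.3 are left out because the documents give no variances for them. If the limits were read as odds ratios instead, every non-significant increase at 40% would be labelled a trend, so the scale needs to be stated.

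**What to change.** Amend SAP 4.12 and Protocol 11.1 together, with an entry in SAP Appendix B. Keep all thresholds, and state that the limits are on the relative-risk scale. Remove the trend wording from both lists and use the following.

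**Increases that are not significant**
- Upper limit > 1.3: *no significant increase; an increase above 30% is not excluded.*
- > 1.2 and ≤ 1.3: *an increase above 30% is excluded, above 20% is not.*
- ≤ 1.2: *an increase above 20% is excluded.*

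**Decreases that are not significant**
- Lower limit < 0.7: *no significant decrease; a decrease above 30% is not excluded.*
- ≥ 0.7 and < 0.8: *a decrease above 30% is excluded, above 20% is not.*
- ≥ 0.8: *a decrease above 20% is excluded.*

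Beside each band report the risk ratio, the p-value and the one-sided 95% limit. Add a two-sided 90% interval for increases and a two-sided 95% interval for decreases; the latter matches the p < 0.025 test, so that a decrease reported as not significant is not printed next to an interval excluding 1.

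**Cost.** Text only; model, data and thresholds are unchanged. The wording would depart from the labels that the plan attributes to GRADE, and a possible missed harm would no longer be flagged by the word trend. The statement that an increase above 30% is not excluded keeps that warning.

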#### 4.13 Analysis of secondary outcome variables

We will estimate and test for the detrimental effects of prednisolone on bone mass and incident fracture rate.

1. Continuous outcomes: bone mass lumbar spine, bone mass hip: analyzed according to model 1
2. Discrete outcome: presence of at least one incident compression fracture (by VFA or lateral spine films): analyzed according to model 2

Tests will be one-sided at  $p < 0.05$ , with Benjamini-Hochberg adjustment for multiple testing.

We will report the results of the other secondary outcome variables descriptively with means/proportions and 95%CI per treatment group per time point.

3. Variables measured at every clinic visit
  - a. Continuous outcomes: patient and physician global assessment of disease activity, joint counts (swollen joints and tender joints), acute phase reactants (C-reactive protein (CRP) and erythrocyte sedimentation rate (ESR)); vital signs, lab (blood) variables; adherence by pill count and by electronic adherence cap.
  - b. Discrete outcomes: patients with at least one instance of remission; of minimal disease activity; patients with at least one long-term period (2 consecutive instances 6 months apart) of remission; of minimal disease activity
4. Variables measured at every visit (clinic and remote):
  - a. Continuous outcomes: severity and duration of morning stiffness, RA Impact of disease (total score, and components pain and fatigue analyzed separately), RAPID3 index, EuroQoL, m(HAQ)
  - b. Discrete outcomes: discontinuations of study drug, of with reason; all changes of antirheumatic treatment, with reason; joint replacement surgery
  - c. Expressed as survival curve: discontinuation of study drug over time
5. Variables measured at baseline and end of study:
  - a. Continuous outcomes: DAS44, SF36 (domains and summary mental and physical component scores), 57-symptom list;
  - b. Discrete outcome: number of incident compression fractures (by VFA or lateral spine films)
6. Variables measured only at baseline:
  - a. Continuous/discrete: Demographics, education and medical history; Morisky medication adherence scale (MMAS-8), health literacy, arthritis helplessness index questionnaires; number of prevalent vertebral fractures (by VFA or lateral spine films), distribution of % height loss in vertebrae with fractures.
7. Response indices calculated at 3 months in the PP analysis (discrete): ACR20, 50, 70; EULAR response.

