### *Harm*

- Vital signs (heart rate and blood pressure), height, weight – at 0, 3, 6, 12, 18, 24, 27 months
- Bone mass assessed by Dual-energy X-ray Absorptiometry (DEXA) - at 0 and 24 months
- Vertebral Fracture Analysis (by DEXA OR lateral radiograph of thoracic and lumbar spine) - at 0 and 24 months
- Discontinuation of study drug with reason: this includes patients in whom treatment with prednisolone becomes clinically indicated or those with unacceptable side effects attributable to study medication
- Change of antirheumatic treatment, with reason
- Intensification of treatment for existing comorbidity, e.g. hypertension or diabetes
- Joint replacement surgery
- AEs, SAEs, other AESI at every study visit
- Concomitant medication at every study visit

Data collection is in agreement with industry standard (i.e. Meddra terminology etc.).

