#### 4.10.1.1 Full model

We model the treatment outcome by a mixed effect model with fixed effects measurement occasion after baseline (d), baseline measurement (Z), treatment condition (T), and random effects across individuals (level 2; random intercept U) and study centers (level 3; random intercept V).

Furthermore, we include the strata of the GLORIA trial (S) as fixed effects. Centers could also be modeled as fixed effects, but we have chosen random effects because several centers have included only a very low number of patients. A compound symmetry correlation structure is assumed.

We write down mixed effect model 1 as:

$$\begin{aligned}
 Y_{ijk} &= \beta_{0jk} + \sum_{s=1}^4 \beta_{1jks} d_{ijks} + \epsilon_{ijk} && \text{(level-1 model)} \\
 \beta_{0jk} &= \delta_{00k} + \delta_{01k} S_{jk1} + \delta_{02k} S_{jk2} + \delta_{03k} T_{jk} + \delta_{04k} Z_{jk} + U_{0jk} && \text{(level-2 model for intercept)} \\
 \beta_{1jks} &= \delta_{10ks} && \text{(level-2 model for slope)} \\
 \delta_{00k} &= \gamma_{000} + V_{00k} && \text{(level-3 model for intercept)} \\
 \delta_{01k} &= \gamma_{010} && \text{(level-3 model for slope)} \\
 \delta_{02k} &= \gamma_{020} && \text{(level-3 model for slope)} \\
 \delta_{03k} &= \gamma_{030} && \text{(level-3 model for slope)} \\
 \delta_{04k} &= \gamma_{040} && \text{(level-3 model for slope)} \\
 \delta_{10ks} &= \gamma_{100s} && \text{(level-3 model for slope)}
 \end{aligned}$$

with  $U_{0jk}$  the individual-level random effect,  $V_{00k}$  the center-level random effect, and  $\epsilon_{ijk}$  the residual.

The indices:

- i= 1,..., m : fixed measurement occasion after baseline (in GLORIA, m=5)
- j= 1,...,n : individuals
- k=1,...,K : study centers (currently, K=28 in GLORIA)

The variables:

- $Y_{ijk}$  : DAS28 outcome
- $d_{ijks}$  : dummy variables encoding the five measurement occasions after baseline, s=1,..., 4
- $T_{jk}$  : treatment indicator, 0 if placebo, 1 if active (prednisolone) treatment
- $Z_{jk}$ : Baseline measurement of DAS28
- $S_{jk1}, S_{jk2}$ : Stratification factors

The parameters:

- $\gamma_{000}$ : the model intercept
- $\gamma_{010}$ : fixed effect of stratification factor 1
- $\gamma_{020}$ : fixed effect of stratification factor 2
- $\gamma_{030}$ : fixed effect of treatment
- $\gamma_{040}$ : fixed effect of baseline measurement of DAS28
- $\gamma_{100s}$ : effect of time dummy s

And the random effects :

- $U_{0jk}$  : random intercept of individual i

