#### 4.10.2 Model and statistical test for the effect of treatment on damage score (hypothesis 2)

The treatment effect on the damage score at 24 months (hypothesis 2) will be evaluated by the total Sharp/van der Heijde damage score of hands and forefeet. We will use a linear mixed-effects regression model defined similarly to model 1. Contrary to model 1 there are no repeated measurements. Therefore, we model outcomes of individuals nested in centers and include as main effects treatment, design strata, and the baseline measurement of the damage score. A random effect for study center is included. Model 2 is formalized as follows:

$$\begin{aligned}
 Y_{jk} &= \delta_{0k} + \delta_{1k}S_{jk1} + \delta_{2k}S_{jk2} + \delta_{3k}T_{jk} + \delta_{4k}Z_{jk} + U_{jk} && \text{(level-1 model)} \\
 \delta_{0k} &= \gamma_{00} + V_{0k} && \text{(level-2 model for intercept)} \\
 \delta_{1k} &= \gamma_{10} && \text{(level-2 model for slope)} \\
 \delta_{2k} &= \gamma_{20} && \text{(level-2 model for slope)} \\
 \delta_{3k} &= \gamma_{30} && \text{(level-2 model for slope)} \\
 \delta_{4k} &= \gamma_{40} && \text{(level-2 model for slope)}
 \end{aligned}$$

where now  $Y_{jk}$  is the damage score at 24 months and  $Z_{jk}$  is the damage score at baseline. Equivalent to section 3.1.1, it can be see that if a one-sided t-test of  $\gamma_{30} < 0$  is significant,  $H_{0,2}$  is rejected.

We note that the damage progression measurement can be positively skewed, threatening the accuracy (type 1 error rate) of the statistical tests in small samples (and other tests of regression coefficients including t- and F-tests). If we observe a strongly skewed distribution we will apply a bootstrapped test procedure instead of the t-test.

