#### 4.10.3 Model and statistical test for the effect of treatment on harm: SAEs or other AESIs (Hypotheses 3)

Contrary to the hypothesis set 1 on the benefit of prednisolone treatment, hypotheses 3 require testing the difference in probabilities of encountering at least one SAE or other AESI over 24 months. On marginal level it would be sufficient to estimate these probabilities after  $t=24$  months and evaluate the significance of their difference. However, to additionally account for the stratification of the GLORIA design, we apply a logistic mixed-effects regression (model 3):

$$P_{jk} = g^{-1}(\delta_{0k} + \delta_{1k}S_{jk1} + \delta_{2k}S_{jk2} + \delta_{3k}T_{jk} + U_{jk})$$

$\delta_{0k} = \gamma_{00} + V_{0k}$	(level-2 model for intercept)
$\delta_{1k} = \gamma_{10}$	(level-2 model for slope)
$\delta_{2k} = \gamma_{20}$	(level-2 model for slope)
$\delta_{3k} = \gamma_{30}$	(level-2 model for slope)
$\delta_{4k} = \gamma_{40}$	(level-2 model for slope)

where now  $P_{jk}$  the probability of patient  $j$  in center  $k$  to encounter at least one SAE or other AESI over 24 months. The function  $g^{-1}$  denotes the inverse of the log link. Significance of  $\delta_{3k}$  will be evaluated with a t-test. Note that model 3 uses the log link as opposed to, for example, the logit link to estimate and test relative risk.

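### SAP 4.13 points its three adjusted bone-harm tests to the wrong models: bone mass fits model 2 and incident fracture fits model 3, not models 1 and 2

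*SAP*

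**What the plan says.** SAP 4.13 singles out bone outcomes for formal testing, one-sided at 0.05 with Benjamini-Hochberg adjustment, and reports the other secondary variables listed there descriptively. There are three such tests:

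- Lumbar spine and hip: "bone mass lumbar spine, bone mass hip: analyzed according to model 1".
- Fracture: "presence of at least one incident compression fracture (by VFA or lateral spine films): analyzed according to model 2".

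The three models are defined in SAP 4.10:

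- **Model 1** (4.10.1.1) is the repeated-measures DAS28 model. Its first index is "fixed measurement occasion after baseline (in GLORIA, m=5", coded by four dummies. It also has "random effects across individuals (level 2; random intercept U) and study centers (level 3; random intercept V", plus a residual.
- **Model 2** (4.10.2) is a linear mixed model for the 24-month damage score, with the baseline damage score as covariate, the strata and a random center effect. The SAP says of it: "Contrary to model 1 there are no repeated measurements".
- **Model 3** (4.10.3) is for the binary harm outcome: "we apply a logistic mixed-effects regression (model 3". The section then specifies a log link, so that the result is a relative risk.

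On timing, the harm list in SAP 1.4.2 gives "Bone mass assessed by Dual-energy X-ray Absorptiometry (DEXA) - at 0 and 24 months", and vertebral fracture analysis has the same two time points. Table 32 in SAP section 7 agrees.

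**The concern.** The model numbers in 4.13 look shifted by one. Bone mass has the data structure that model 2 was written for: one 24-month value and its baseline. Incident fracture has the structure that model 3 was written for: one yes/no result per patient.

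This matters because the plan commits itself to testing for bone harm, in a trial about the balance of benefit and harm of a glucocorticoid. An analyst who follows 4.13 to the letter meets a model with terms that cannot be estimated for two of the tests. For the third, the model treats a yes/no outcome as a continuous score. The analyst must then choose a model without written authority, and a choice made after unblinding could look post hoc.

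**Working it through.** The documents give no power, rate or expected difference for bone mass or fracture, so there is no stated figure to reproduce. The check is of the model structure, with a simulation to size the effect on the fracture test.

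**Bone mass under model 1**

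Fixed effects: the intercept, two strata, treatment and baseline make 5 columns, and the four occasion dummies bring this to 9. When only month 24 is observed, each dummy is constant over all patients (0 or 1), so it is either empty or a copy of the intercept. The computed rank is 5, so no occasion effect can be estimated.

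Random effects: with one value per patient,

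Var(Y) = σ²_V + (σ²_U + σ²_ε), and Cov = σ²_V for two patients in the same center.

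Only the sum σ²_U + σ²_ε enters the likelihood. As a check, one data set of 450 patients in 28 centers was simulated. Assumed values were baseline mean 0.95 and SD 0.15, center SD 0.01, error SD 0.04 and treatment effect −0.01. The log-likelihood (up to a constant) was 1207.546 whether the patient intercept took 0%, 10%, 50% or 90% of the within-center variance. The treatment estimate (−0.0146) and its standard error (0.0038) were also the same at every split.

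The patient variance and the occasion terms are therefore not identified, but the treatment effect is untouched once they are removed. What remains is model 2 with bone mass in place of the damage score.

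**Incident fracture under model 2**

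The outcome is 0 or 1, so the treatment coefficient of a linear model is a risk difference. The baseline covariate of model 2 is the damage score at baseline. SAP Appendix A defines an incident fracture as a worsening from the baseline grade, so the outcome has no baseline value of its own to use there.

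The linear fit was compared with a Wald test of the log relative risk at 225 per arm, one-sided 5%, 4000 runs per row. All fracture rates are assumptions. The linear fit had strata and treatment but no center effect or baseline covariate. The relative-risk test was unadjusted and stands in for model 3.

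| Placebo / prednisolone rate | Relative risk | Mean linear coefficient | Rejection, linear | Rejection, log relative risk | Fits with a negative fitted probability |
|---|---|---|---|---|---|
| 3% / 3% | 1.0 | −0.0002 | 4.5% | 4.0% | 14.2% |
| 8% / 8% | 1.0 | −0.0001 | 5.3% | 5.0% | 0.2% |
| 15% / 15% | 1.0 | −0.0003 | 4.9% | 4.7% | 0% |
| 3% / 6% | 2.0 | 0.030 | 46% | 44% | 13.2% |
| 8% / 12% | 1.5 | 0.041 | 42% | 42% | 0.2% |
| 15% / 22% | 1.47 | 0.069 | 59% | 59% | 0% |

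The simulation error at a true 5% is √(0.05 × 0.95 / 4000) = 0.34 percentage points, so the type I error rates of the linear test are compatible with 5%.

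The reason is the equal allocation. At 3% and 6% the arm variances are 0.03 × 0.97 = 0.0291 and 0.06 × 0.94 = 0.0564, almost twofold apart. A common variance is then about their average, and 2 × average / 225 equals (0.0291 + 0.0564) / 225. The standard error of the difference hardly changes. What changes is the scale: a difference of 0.030 is reported where model 3 would report a ratio of 2.0.

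**The case against.** The strongest reply is that this is a slip in numbering that any competent analyst would see through, and much of that stands.

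- **Bone mass.** A reader might infer that the analysis cannot be done at all. The SAP does not support that. The end of 4.10.1.1 reduces model 1 to two levels without time for the 3-month per-protocol analysis, because there is only one post-baseline assessment, and the same reason applies here. The gap is that neither that section nor 4.13 says so for bone mass.
- **Fracture test.** A reader might infer an invalid test with an inflated error rate. Under the assumed rates it is not.
- **Effect measure.** 4.13 names none for fracture, and Protocol 11.1 plans both absolute and relative risks for major events. A risk difference is therefore not foreign to the plan. It does differ from the relative risk on which SAP 4.9.1 and 4.12 read the primary harm outcome.
- **Baseline covariate.** Prevalent vertebral fractures are recorded at baseline and could serve, but the SAP does not say that they will.
- **Trial conclusion.** A reader might infer that the overall verdict is at risk. It is not: the rules in 4.12 use DAS28, damage, co-intervention and SAE or other AESI, not bone outcomes.
- **Reach.** These are not the only tested secondary outcomes, since SAP 4.8.2 tests DAS28 at 3 months. They are the ones tested under the Benjamini-Hochberg adjustment.

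Other outdated cross-references favor a slip as the cause: SAP 4.2 places model 3 in a section 3.3, and 4.10.2 refers back to a section 3.1.1. That explains the error without correcting it.

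**Conclusion.** The point holds in a limited form. All three adjusted tests in SAP 4.13 carry a model reference that does not match the outcome.

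For bone mass this is an error of specification with no numerical effect, provided the analyst makes the two-level reduction that the SAP leaves unstated for this outcome. For fracture it has more substance: a linear fit with a common error variance, an undefined baseline covariate, an estimate and interval on the difference scale, and, at rates near 3%, negative fitted probabilities in about 13% to 14% of fits.

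The finding that the fracture test stays close to nominal rests on assumed null rates of 3% to 15%, 225 per arm and a comparison without center effects or a baseline covariate. Patients without a 24-month spine image would reduce the numbers; that was not modeled.

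This should be corrected, but it does not threaten the trial's main conclusions.

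**What to change.** In SAP 4.13:

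1. Send lumbar spine and hip bone mass to model 2: the 24-month value as outcome, and baseline bone mass at the same site as covariate.
2. Send presence of an incident compression fracture to model 3, stating the log link and the relative risk in words. The wording matters because 4.10.3 also calls the model logistic and lists a fourth slope that its equation does not contain, and the introduction to 4.10 speaks of an odds ratio. The number alone would not settle the effect measure.
3. State whether prevalent vertebral fracture at baseline is a covariate.

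The cost is a few words, with no new data and no change in design. There is one small downside: a log-link model with random effects for 28 centers, several of them very small according to 4.10.1.1, may be hard to fit if fractures are rare. A fallback named in advance would cover that. If the blind is already broken, the change should be recorded as a correction of a reference, with its date.
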